#### **Research Protocol**

## I. Aims

The purpose of the study is to evaluate the efficacy of Ropinirole in treatment of muscle cramps in patients with cirrhosis.

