## **II. Background and Rationale**

Muscle cramps are common in liver disease, especially in patients with cirrhosis. The prevalence of muscle cramps among patients with chronic liver disease is estimated to be 22-88%. Patients with cirrhosis who experience muscle cramps report that they are extremely painful and they often occur at rest and frequently during sleep. The severity of muscle cramps in some patients has resulted in presentation to an acute care facility for pain relief with short acting opioids. Muscle cramps impact many areas of life including sleep, physical functioning and mobility, general health, mental health, energy levels and social isolation. Despite the association of muscle cramps with liver disease, there is a paucity of information regarding treatment in these patients. Many treatment options have been reported in the literature but no standard of treatment has been established. Different options include Zinc, 1-alpha-hydroxy Vitamin D, Vitamin E, branched chain amino acids, taurine, L-carnitine, eperisone hydrochloride, intravenous albumin and quinidine. Oral vitamin E replacement has been used successfully in the management of nocturnal muscle cramps in cirrhotic patients. In a group of 23 cirrhotic patients (16 and 7 Child's-Pugh category A and B respectively), oral vitamin E (tocopherol acetate) 200 mg t.i.d. significantly improved the frequency, duration and pain associated with nocturnal cramping without untoward effects. Quinine and quinidine have also been used with success in the treatment of cirrhosis-associated muscle cramps, but their potential for cardiac and gastrointestinal toxicity make them less desirable therapeutic choices. Similarly, another study comparing the effect of 325 mg of quinine versus vitamin E 400 IU at bedtime found reduction in frequency of leg cramps to 3.6 and 3.3% respectively (95% confidence interval, -3.8, +3.2), suggesting similar efficacy. Considering the potential toxicity of quinine, vitamin E is recommended as the initial treatment of choice for patients on dialysis with leg cramps. Our aim is to compare the efficacy of Ropinirole, to Vitamine E in the treatment of these cramps in cirrhotic patients. Ropinirole is primarily used for treatment of restless leg syndrome. However, off label trial of low-dose Ropinirole in clinical practice has shown some success in providing relief of muscle cramps in patients with cirrhosis.

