### . Procedures

A. Research Design: Prospective Randomized cross-over design

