## B. Sample

- a. Number of subjects: 60; 30 in Group A; 30 in Group B
- b. Inclusion criteria: Patients age >/= 18 years of age with diagnosis of cirrhosis who self-report regular muscle cramping.
- c. Exclusion criteria: patients without cirrhosis, patients under age 18, pregnant women

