### C. Study procedures

- a. Patients will be recruited from a panel of patients at Vanderbilt University Medical Center Hepatology clinics. Patients meeting inclusion criteria will be randomized to two groups; group A (Vitamin E 400 I.U) or group B (Ropinirole). Patients will remain in their prospective groups until 3 months at which time they will be switched to the other group. Total study duration will be six months. Patient demographics to be collected include patient age, gender, height, weight, BMI, race/ethnicity, etiology of cirrhosis. Baseline lab data to be collected include Magnesium, Potassium, Albumin, and total bilirubin. Child-Turcotte-Pugh class will be calculated using the five measures of severity of chronic liver disease (Total bilirubin, INR, albumin, presence of ascites or hepatic encephalopathy). Baseline data regarding diuretic usage including Furosemide, Spironolactone, Bumex, Metolazone, Inspra will be obtained. A survey (attached) will be given to each group of patients in the beginning of the study period and 3 and 6 months after study initiation.
- b. Participants will be given a prescription for Ropinirole. Vitamin E will be provided by the GI clinical research office at no cost to the patients.
- c. Adverse event reporting: Serious adverse events will be reported to the VU IRB per VU IRB policy. All adverse events will be captured and reported to the VU IRB at the time of continuing renewal or upon study closure, whichever occurs first.
- d. Withdrawal procedures: If a patient suffers an adverse event, which in the judgment of the investigator is an unacceptable consequence or risk to the patient, the patient can be withdrawn from the study. Patients may withdraw from the study at any time for any reason, and without prejudice to further treatment. A patient can withdraw their consent to participate in the study at their own request or be withdrawn from participation in the study at the request of their legally authorized representative at any time for any reason.
- e. Privacy and confidentiality issues: Consent will be obtained by the study personnel in a private location within the TVC. No PHI will be collected prior to obtaining informed

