consent. The PI and his research staff will have access to this information. Consent forms will be maintained in a locked cabinet in the GI clinical research office. PHI will be collected during the course of this research study from the medical records of consented individuals. Initially, an inclusion log will be created and maintained by the study staff. This log will contain subject initials, medical record numbers, assigned study number and date of inclusion. The only person who will have access to this inclusion log is the PI and study coordinator. The data collected will be entered into a REDCap database (attached) and will not include any information that could link the data to a specific individual. This database will be maintained by the research staff and raw data as well as results will be held by the GI Clinical Research Office indefinitely. The PI, other key study staff and statistician will have access to the REDCap database.

- f. Follow up: patients will have follow up at 3 and 6 months after initiation of the study followed by their regularly scheduled appointments after completion of the study.
- **D. Data Analysis:** paired t-test will be used for data analysis. Preparation of data listings, tables, and overall statistical support for generation of the data will be managed independently by a statistician who will remain isolated from the clinical personnel involved in the study operations.

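### The planned paired t-test makes no allowance for period in a two-period cross-over; a period-adjusted comparison of the same data is more precise and guards against bias

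*Combined protocol and SAP*

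**What the plan says.** The design, under Procedures, item A, is a "Prospective Randomized cross-over design". Item B gives the size and split: "Number of subjects: 60; 30 in Group A; 30 in Group B". Group A starts on vitamin E and Group B on ropinirole. Under item C.a, "Patients will remain in their prospective groups until 3 months at which time they will be switched to the other group", and the survey is given "in the beginning of the study period and 3 and 6 months after study initiation". The 3- and 6-month surveys are therefore the two end-of-period measurements.

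Section II states the comparison of interest: "Our aim is to compare the efficacy of Ropinirole, to Vitamine E in the treatment of these cramps in cirrhotic patients".

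Item D, Data Analysis, contains one statement of method: "paired t-test will be used for data analysis". Its only other sentence is about who prepares the listings and tables. Period and sequence are not mentioned there or elsewhere in the supplied text. Item C.d adds that "Patients may withdraw from the study at any time for any reason"; no dropout rate is given.

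**The concern.** In a cross-over each patient's drug difference is also a difference between two times. Cramps may ease or worsen over six months for reasons unrelated to the drugs, and patients may answer a repeated survey differently. Such a shift adds to the ropinirole-minus-vitamin E difference in one sequence and subtracts from it in the other. Randomising the order allows the two to be separated, but only if the analysis uses the sequences. A plain paired t-test puts all the differences in one pool.

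Two things follow. With equal sequences the shifts cancel in the mean but remain in the spread, so the standard error is too large and power is lost. With unequal sequences they do not cancel in the mean either, and part of the period effect is counted as drug effect.

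**Working it through.** **Inputs from the documents.** Two sequences of 30 (item B), two 3-month periods with end-of-period surveys at 3 and 6 months (item C.a), and a paired t-test (item D). The documents give no significance level, power, effect size, SD or dropout rate, so the plan has no figure of its own to reproduce.

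**Assumptions.** Two-sided 5%; normally distributed paired differences with SD 1 within each sequence; no carry-over; period effect p of 0, 0.25, 0.5 or 1.0 SD of the paired difference; true drug difference τ = 0.37 SD for power. The value 0.37 is used because it is about what 60 pairs can detect with 80% power.

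**Model.** Let d be ropinirole minus vitamin E within a patient, and p the shift from period 1 to period 2.
- Group A (vitamin E first): mean of d is τ + p.
- Group B (ropinirole first): mean of d is τ − p.

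**Plain paired t-test.** Its estimate is the mean of all d, with expectation τ + p(nA − nB)/(nA + nB).

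At 30:30 the bias is p × 0/60 = 0. The expected pooled variance of d, however, is 1 + (60/59)p², not 1:
- p = 0.25: 1 + 1.017 × 0.0625 = 1.064, SD 1.03
- p = 0.5: 1 + 1.017 × 0.25 = 1.254, SD 1.12
- p = 1.0: 1 + 1.017 × 1 = 2.017, SD 1.42

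The reported standard error is thus about 3%, 12% or 42% larger than it need be.

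**Period-adjusted analysis.** Take each patient's 6-minus-3-month difference. Its mean is τ + p in Group A and −τ + p in Group B. Half the difference between the two means is [(τ + p) − (−τ + p)]/2 = τ, so p drops out whatever the numbers completing. The test has nA + nB − 2 degrees of freedom.

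**Results at 30:30.** With no period effect, the noncentral t with noncentrality 0.37 × √60 = 2.87 gives 80.5% power for both tests (59 and 58 degrees of freedom). The other entries are from simulation.

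| Period effect (SD) | Plain: power | Adjusted: power | Plain: false positives | Adjusted: false positives |
|---|---|---|---|---|
| 0 | 80.5% | 80.5% | 5% | 5% |
| 0.25 | 79% | about 80.5% | 4% | 5% |
| 0.5 | 73% | about 80.5% | 3% | 5% |
| 1.0 | 51% | about 80.5% | 0.6% | 5% |

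**Results with unequal completers, period effect 0.5 SD, no drug effect.**

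| Completers | Bias of plain test | Plain: false positives | Adjusted: false positives |
|---|---|---|---|
| 30:25 | 0.5 × 5/55 = 0.045 SD | 4% | 5% |
| 30:20 | 0.5 × 10/50 = 0.10 SD | 7% | 5% |
| 30:15 | 0.5 × 15/45 = 0.17 SD | 14% | 5% |

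With a period effect of 0.25 SD the plain test rejects in 5%, 6% and 8% of trials at the same three splits.

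**Cost of adjusting when there is no period effect.** The ratio of standard errors, adjusted to plain, is [√(1/nA + 1/nB)/2] × √(nA + nB). This is 1.000 at 30:30, 1.021 at 30:20 and 1.061 at 30:15.

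**The case against.** A paired t-test is a recognised analysis of a balanced cross-over. The planned split is equal, and at that split the test is unbiased and, if anything, conservative. Inflation of the false-positive rate needs one sequence to lose a third or a half of its patients while the other loses none. No dropout rate is given, and the withdrawal clause is ordinary consent wording that predicts no imbalance. All of this stands. It means that bias is the secondary reason for the change. It does not answer the loss of precision, which arises at 30:30 with no dropout at all.

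A reader might also infer more than the text supports:

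- *That a before-after test is planned.* Section I aims only to "evaluate the efficacy of Ropinirole in treatment of muscle cramps in patients with cirrhosis" and names no comparator, and the survey is also given at baseline. But the comparative aim in Section II, the cross-over and the 3-month switch together imply ropinirole versus vitamin E at the two period ends. No section plans a comparison with baseline.
- *That several survey items will each be tested at 5%.* The survey is an attachment that was not available for this review. Its number of items is unknown, and it may yield a single score. No false-positive rate for multiple items can be derived from the documents.
- *That the lack of a named primary outcome and significance level is itself the fault.* Naming them would be good practice, but it is pre-specification detail and this point does not depend on it.

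**Conclusion.** The point holds as an inexpensive improvement to the analysis; it does not show that the planned test is invalid. At 30:30 the plain paired t-test gives an unbiased estimate with an overstated standard error whenever there is a period effect. On the stated assumptions it loses about 2, 8 and 30 percentage points of power at period effects of 0.25, 0.5 and 1.0 SD (80.5% to 79%, 73% and 51%). The adjusted analysis loses essentially none.

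Protection against bias comes second. It matters only if completion is strongly unequal between sequences, about 30:20 or worse, and a period effect is present.

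That the plan has no period term is certain from the text. The size of the consequence is not: the period effect, drug effect, SD and completion rates are all assumed, and with no period effect the two tests perform almost identically at 30:30. Carry-over is excluded from these calculations and is a separate point that a period term does not address.

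**What to change.** In Data Analysis, before any data are reviewed, replace the plain paired t-test with wording such as:

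> The drug comparison is within patient, between the survey values at the end of the ropinirole period and the end of the vitamin E period (3- and 6-month surveys), with allowance for period. The 6-minus-3-month differences are compared between the two sequences by a two-sample t-test; half the difference in means (vitamin E first minus ropinirole first) estimates the effect of ropinirole relative to vitamin E. The estimate is reported with a 95% confidence interval.

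A linear model with patient, period and drug terms would serve equally well. It is sensible to name one survey item or score as primary, and the significance level, in the same place.

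The change uses only surveys already scheduled and needs no extra patients or visits. At 30:30 it costs one degree of freedom (59 to 58). If there is no period effect, the standard error is about 2% larger at 30:20 completers and 6% larger at 30:15.
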